1 DEFINITIONS AND ABBREVIATIONS

Term	Description
ADE	Adverse Device Effect
AE	Adverse Event
AMDT	Approved Medical Device on Test
CER	Clinical Evaluation Report
CIP	Clinical Investigation Plan
CIR	Clinical Investigation Report
CRF	Case Report Form
DCF	Data Clarification Form
DD	Device Deficiency
EC	Ethics Committee Synonymous abbreviations/terms include: IRB (Institutional Review Board) IEC (Institutional Ethics Committee or Independent Ethics Committee) HREC (Human Research Ethics Committee)
eCRF	Electronic Case Report Form
EDC	Electronic Data Capture
EOS	End of Study
GCP	Good Clinical Practices
ICF	Informed Consent Form
IDMC	Independent Data Monitoring Committee
NCA	National Competent Authority
PI	Principal Investigator
PIL	Principal Investigator List
PMS	Post-Market Surveillance
SADE	Serious Adverse Device Effect

Term	Description
SAE	Serious Adverse Event
SAP	Statistical Analysis Plan
SOP	Standard Operating Procedure
UADE	Unanticipated Adverse Device Effect
USADE	Unanticipated Serious Adverse Device Effect

2 CLINICAL INVESTIGATION SYNOPSIS

Investigation title	A post-market interventional, cohort study evaluating the clinical efficacy of the Osia 2 system in the US Market.
Short title	Osia 2 CPT Code Study.
Investigation number	CAM 5778
Name of investigational medical device(s)	Osia 2 Active Osseointegrated Implant System for Bone Conduction.
Intended use of investigational medical device(s)	Treatment of conductive and mixed conductive hearing loss in adults aged 18 years and older with bone conduction PTA4 (.5, 1, 2, and 3kHz) better than or equal to 55 dBHL in the treated ear.
Name and description of comparator device/product(s)	Reference device: Baha 5 Power sound processor on the Baha Sound Arc.
Expected start date (first subject consented)	July 2020
Expected enrolment period	6 – 8 months.
Expected duration per subject	7 – 8 months.
Expected total duration of the clinical investigation	12-18 months.
Number of subjects planned	Up to 20 Newly Implanted Osia 2 subjects.
Number of investigational sites planned	Up to 6 US sites.
Inclusion criteria	
 • Willing and able to provide written informed consent. • Proficient in English. • Hearing loss etiology of Conductive or Mixed Conductive loss. • Bone conduction PTA (.5, 1, 2, and 3kHz) better than or equal to 55dB HL in the treatment ear. • Aged 18 years and older.

Exclusion criteria	
 • Unwilling to wear the treatment device or comply with the surgical and rehabilitation requirements of the study. • Unable or unwilling to comply with the requirements of the clinical investigation as determined by the Investigator. • Medical, audiological or psychological conditions, as judged by the investigator that might contraindicate participation in the clinical investigation. • Investigator site personnel directly affiliated with this study and/or their immediate families; immediate family is defined as a spouse, parent, child, or sibling. • Cochlear employees or contractors engaged by Cochlear for the purposes of this investigation. • Currently participating, or participated within the last 30 days, in another interventional clinical investigation/trial involving an investigational drug or device. • Prior experience with a surgical bone conduction treatment option. • Insufficient bone quality to support the BI300 implant as determined by the surgeon.
Primary objective(s)	To evaluate the performance of the Osia 2 system on an adaptive speech in noise test.
Secondary objective(s)	To evaluate the safety of the Osia 2 system in a group of adult newly implanted recipients.
Exploratory objective(s)	Not applicable.
Primary endpoint(s)	To demonstrate significant difference between the aided and unaided conditions at 3 months using an adaptive speech in noise test when compared to the preoperative (Visit 1) unaided condition.
Secondary endpoint(s)	To evaluate the safety of the Osia 2 system in a group of adult newly implanted recipients by estimating the incidence of device or procedure related adverse events.
Exploratory endpoint(s)	Not applicable.

3 SCHEDULE OF EVENTS

	Screening	Visit 1	Visit 2	Visit 3	Visit 4	Visit 5	Visit 6 EOS
Timing of Investigation	Day -1	Day -1	Day 0	Week 2	Week 4	Month 3	Month 6
Visit window (±)	NA	± 0 days	± 0 days	± 5 days	± 7 days	± 7 days	± 7 days
Time Estimation	2 hrs. 15 mins.	3 hrs. 15 mins	1 hr.	1 hr.	3 hrs.	4 hrs.	3 hrs.
Written informed consent	X						
Demographics	X						
Inclusion/Exclusion	X						
Hearing history	X						
Medical history	X						
Audiogram	X						
Concomitant Medications ¹		X	X	X	X	X	X
Sound field thresholds		X ²			X ³	X ⁴	X
Speech perception testing in quiet		X ⁵			X ⁶	X ⁷	X

¹ Collected post-Visit 1 only if changes to prescription concomitant medications associated with device or procedure-related adverse event.

² Includes sound field thresholds, unaided and aided, with Baha 5 Power on Sound Arc.

³ Visits 4 & 6 include sound field thresholds, aided, with Osia Sound Processor.

⁴ Visit 5 includes sound field thresholds, unaided and aided, with Osia Sound Processor.

⁵ Includes speech in quiet testing, unaided and aided, with Baha 5 Power on Sound Arc.

⁶ Visits 4 & 6 include speech perception in quiet, aided, with Osia Sound Processor.

⁷ Visit 5 includes speech perception in quiet, unaided and aided, with Osia Sound Processor.

	Screening	Visit 1	Visit 2	Visit 3	Visit 4	Visit 5	Visit 6 EOS
Timing of Investigation	Day -1	Day -1	Day 0	Week 2	Week 4	Month 3	Month 6
Visit window (±)	NA	± 0 days	± 0 days	± 5 days	± 7 days	± 7 days	± 7 days
Time Estimation	2 hrs. 15 mins.	3 hrs. 15 mins	1 hr.	1 hr.	3 hrs.	4 hrs.	3 hrs.
Speech perception testing in noise +5 dB SNR		X ⁸				X ⁹	
Adaptive speech in noise testing		X ¹⁰			X ¹¹	X ¹²	X
SSQ 12		X				X	
Patient Reported Questionnaire		X				X	
Device Counseling		X			X		
Surgical Follow up				X			
Fitting and Optimization of Sound Processor		X ¹³			X ¹⁴	X	X
Device Deficiencies			X	X	X	X	X
Adverse Events			X	X	X	X	X
Data Entry	X	X	X	X	X	X	X

⁸ Includes speech perception in noise, unaided and aided, with Baha 5 Power on Sound Arc.

⁹ Visit 5 includes speech perception in noise, unaided and aided, with Osia Sound Processor.

¹⁰ Includes adaptive speech in noise testing, unaided and aided, with Baha 5 Power on Sound Arc.

¹¹ Visit 4 & 6 include adaptive speech in noise testing, aided, with Osia Sound Processor.

¹² Visit 5 includes adaptive speech in noise testing, unaided and aided, with Osia Sound Processor.

¹³ Fitting with Baha 5 Power on Sound Arc.

¹⁴ Fitting with Osia Sound Processor.

4 BACKGROUND INFORMATION AND RATIONALE

4.1 Introduction

Bone conduction implant systems are designed to provide aural rehabilitation for individuals with moderate to severe conductive (CHL) or mixed (MHL) hearing losses or single-sided sensorineural deafness (SSD). The initial bone conduction system relied on percutaneous transmission of sound vibrations from an electromagnetic transducer connected to a skin-penetrating abutment attached to an osseointegrated screw-shaped fixture. Due to the efficient transmission pathway and availability of a range of powerful sound processors, percutaneous implants continue to offer the broadest audiological fitting range and remain the most commonly used bone conduction implant type. In recent years, there has been rapid development of new implantable transcutaneous options for patients in need of a bone conduction hearing solution that maintain efficient transmission but also reduce complication rates due to the percutaneous abutment.

The Osia System is a new active transcutaneous implant system that uses piezoelectric instead of electromagnetic stimulation and is built on the experience gained from both transcutaneous and percutaneous bone conduction systems. The implanted piezoelectric element fixes to bone via an osseointegrated implant similar to current percutaneous devices. The digital sound signal is transferred from the sound processor to the implant through a digital radio frequency (RF) link. Due to this design, the Osia system is able to provide a more efficient transmission of sound, especially in the high frequency range, as the implantable transducer eliminates the attenuation of sound vibrations through soft tissue that is inherent to passive bone conduction systems. The additional high frequency output aids consonant recognition and word discrimination ultimately improving auditory comprehension, especially in noisy environments.

Clearance for the Osia 2 system was supported by a global clinical trial evaluating safety and efficacy in a mixed, mixed conductive and single-sided deaf adult population. Fifty-one (51) adult subjects were included in the investigation and a total of 53 devices were implanted across five investigational sites. The overall study duration per subject was 12 months post implantation with the primary efficacy time point at 3 months post implantation and primary safety at 6 months post implantation. The results are detailed in the Clinical Investigation Report for study CBAS5539 Clinical performance of a new implant system for bone conduction hearing Document No: D1478473.

Upon clearance of the Osia 2 system in the United States, it was determined that the clinical evidence intended to support the reimbursement coverage of the Osia 2 system was inadequate. To further support the reimbursement efforts associated with the Osia 2 system, clinical evidence gathered in the United States will be collected.

4.1.1 Nonclinical Data

A summary of non-clinical data is available for reference in the Osia FDA clearance K190589.

4.1.2 Clinical Data

The outcomes from CBAS5539 Clinical performance of a new implant system for bone conduction hearing are available in Document No: D1478473.

4.2 Study Rationale

As it was determined that the clinical evidence intended to support the reimbursement coverage of the Osia 2 system was inadequate, clinical evidence gathered in the United States will be collected to further support the reimbursement efforts associated with the Osia 2 system.

5 MEDICAL DEVICE INFORMATION

5.1 Identity and Description of the Approved Medical Device on Test (AMDT)

The Osia System is made up of several components. The Osia Implant (OSI200) consists of a receiver/stimulator and an actuator (vibrator) which is surgically implanted on the skull bone. The external component of the Osia System is a sound processor, worn off-the-ear, which picks up the sound from the environment, and sends, after processing, the information to the implant via a transcutaneous inductive link. This link is also referred to as radiofrequency (RF) link. Each Osia System is configured to meet an individual's hearing needs, using dedicated fitting software. The Osia System is illustrated in Figure 1 below.

[figure not shown]

Figure 1: Overview of the Osia System, including the Osia Sound Processor

In normal operation, the Osia System functions as follows (Figure 1):

1. The external sound processor captures and digitally processes sound.
2. The sound processor transmits power and digital information to the implant coil/receiver.
3. The implant stimulator/actuator converts the digital information into an electric analogue signal that is converted to vibrations by the implant piezoelectric actuator.
4. This implant is fixed to the bone by the BI300 implant.

The actuator converts the electrical signal into an amplified mechanical stimulation, bypassing the impaired middle ear (origin of the conductive part of the hearing loss) and providing some level of mechanical amplification in order to compensate for the damaged inner ear (sensorineural part of the hearing loss, in case of mixed hearing loss).

5.2 Identity and Description of the Comparator

The Baha 5 Power will be utilized on a Sound Arc as the pre-surgical reference for the aided test condition. Each subject will be assessed in both the aided and unaided condition pre-operatively and then compared to their performance aided and unaided at the 3 months post- surgical test visit using the AMDT, the Osia 2 system. The signal processing of the Baha 5 Power is most comparable to the Osia Sound Processor and therefore has been chosen as the comparator.

5.3 Accessory Device Requirements

Not applicable.

6 OBJECTIVES

6.1 Primary Objective

To evaluate the performance of the Osia 2 system on an adaptive speech in noise test.

6.2 Secondary Objective

To evaluate the safety of the Osia 2 system in a group of adult newly implanted recipients.

6.3 Exploratory Objective

Not Applicable.

7 DESIGN OF THE CLINICAL INVESTIGATION

7.1 General

A post-market interventional cohort study evaluating the clinical efficacy of the Osia 2 system in the US Market.

The subjects include adults aged 18 years and older who meet the pre-specified study inclusion and exclusion criteria. Up to 20 eligible subjects will be enrolled.

Study subjects will be implanted with the Osia 2 system according to the commercially approved Physicians Guide. Subjects will attend scheduled study visits as described in the CIP Schedule of Events (Section 3). At study visits, subjects will undergo hearing and safety assessments. The primary endpoint is to evaluate the performance of the Osia 2 system on an adaptive speech in noise test. Safety associated with implantation of the Osia 2 system will be assessed by recording and summarizing device or procedure related AEs and DDs. No data monitoring committee will be used for this clinical investigation. An analysis will be conducted once all subjects complete Visit 5. All subjects will attend an End-of-Study visit at the time they complete the study.

7.1.1 Design Rationale

This clinical investigation design ensures that the results obtained have clinical relevance, scientific validity and address the clinical investigation objectives. A within subject research design has been employed to utilize each subject as his or her own control as it accommodates the heterogeneity that characterizes hearing impaired populations.

Subjects seeking treatment with an Osia 2 bone conductive device may present clinically as being aided or unaided, therefore it is important to capture both listening conditions to ensure a representative sample. Since the Osia 2 Sound Processor cannot be utilized in a non- surgical wearing configuration, each subject will be fit with the Baha 5 Power device on a Baha Sound Arc according to the Cochlear Baha Fitting prescription. The Baha 5 Power device is most comparable from a sound processing perspective to the Osia 2 Sound Processor.

A test order randomization paradigm has been employed to minimize test order effects and demonstrate the unaided to aided benefits of bone conduction technology. Due to the physiology of a conductive or mixed conductive hearing loss, there are no carry-over effects associated with the use of an osseointegrated bone conduction intervention and therefore comparisons can be made.

7.2 Subjects

7.2.1 Inclusion Criteria

Subjects must meet all of the inclusion criteria described below to be eligible for this clinical

investigation.

- Willing and able to provide written informed consent.
- Proficient in English.
- Hearing loss etiology of Conductive or Mixed Conductive loss.
- Bone conduction PTA (.5, 1, 2, and 3 kHz) better than or equal to 55 dB HL in the treatment ear.
- Aged 18 years and older.

7.2.2 Exclusion Criteria

Subjects who meet any of the exclusion criteria described below will not be eligible for this clinical investigation.

- Unwilling to wear the treatment device or comply with the surgical and rehabilitation requirements of the study.
- Unable or unwilling to comply with the requirements of the clinical investigation as determined by the Investigator.
- Medical, audiological or psychological conditions, as judged by the investigator that might contraindicate participation in the clinical investigation.
- Investigator site personnel directly affiliated with this study and/or their immediate families; immediate family is defined as a spouse, parent, child, or sibling.
- Cochlear employees or contractors engaged by Cochlear for the purposes of this investigation.
- Currently participating, or participated within the last 30 days, in another interventional clinical investigation/trial involving an investigational drug or device.
- Prior experience with a surgical bone conduction treatment option

Insufficient bone quality to support the BI300 implant as determined by the surgeon

Written, informed consent must be obtained from the subject before any study procedures are initiated.

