7.2.5 Enrollment & Study Duration

The following subject status definitions apply:

Consented: A subject who has provided informed consent and is being assessed for eligibility according to the Screening requirements.

Screen Fail: A consented subject that has been determined to not meet all eligibility criteria for enrolment.

Enrolled/Treated: Subjects who have met all eligibility criteria, have qualified for surgery and have received the Osia 2 implant.

Withdrawn: Enrolled subjects who withdraw or are withdrawn by the Investigator or Sponsor before their expected end of study visits. Withdrawn subjects may still continue in safety follow-up until their scheduled end of study visit for reasons described in section 7.2.6.

The enrollment period for the clinical investigation is anticipated to be 6 - 8 months from the time of first subject consent to enrollment of the last subject.

The expected duration of each subject's participation is 7-8 months.

During this time there will be required research related visits.

- Screening
- Visit 1
- Visit 2: Surgery - Treatment
- Visit 3: 2-week check post-surgery
- Visit 4: 4-week post-surgery fitting
- Visit 5: 3 Months post-surgery
- Visit 6: 6 Months post-surgery (End of Study)

The anticipated total duration of the clinical investigation is therefore 12 - 18 months including set up, execution and closure. The execution phase of the Clinical Investigation is considered complete after the last subject, last visit. IRBs should remain open through closeout monitoring activities, until Sponsor notifies site of database lock.

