8.2.2 Additional Risks Associated with Implantation of the Study Device

- Pain or discomfort
- Skin irritation near the implant, swelling or redness near the magnet site, skin breakdown
- Sense of numbness or stiffness in the area of the surgery
- Failure of the implant to properly anchor to the skull-bone due to a lack of adequate bone quantity/quality, trauma, infection, generalized diseases and surgical complications
- Other medical complications that may require additional medical treatment, such as:
 - Concurrent CSF leakage: a leak of CSF (cerebrospinal fluid) through the hole in the skull
 - Subdural injury: blood vessels near the brain may burst
 - Subcutaneous hematoma: bruises and contusions on the skin
 - Skin-flap infection, irritation or inflammation
 - Extrusion of the device caused by a foreign body under the skin
 - Revision surgery to remove the study implant in the event of device failure
- Failure of the implant or sound processor could result in the perception of an uncomfortably loud sound sensation, intermittent sound, or no sound.
- The implanted magnet may affect MRI (Magnetic Resonance Imaging) procedures. The magnet may influence the MRI scanner or the ability of the scanner to detect certain changes. Under certain circumstances removal of the AMDT may be necessary prior to MRI scanning.
- There may be side effects that are not known at this time.

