14 DATA MANAGEMENT

The CRF will capture subject status according to the following criteria:

- **Consented:** Signed consent and eligibility evaluations underway

- Screen Fail: Subject determined not to be eligible to proceed for participation
- Enrolled/Treated: Subjects who are considered enrolled or treated have been successfully implanted with the AMDT. Any participant who is not successfully implanted will be considered a treatment failure and classified accordingly.
- Withdrawn: Enrolled subjects who withdraw or are withdrawn by the Investigator or Sponsor before the expected End of Study visit.
- Complete: Enrolled subjects who complete the planned follow up schedule and End of Study visit.

Source data will be captured in clinic notes, paper-based source data worksheets, or printed directly from testing software. The Origin of Source Form will be completed for each site prior to first subject consented, to support clear and concise identification of source data at each clinical site. If electronic medical records do not permit read only access for monitoring purposes, a verified printout and/or certified copy must be provided.

Data collection will be performed using [REDACTED] for electronic data capture (EDC) on electronic Case Report Forms (eCRFs). Site staff will be trained on the completion of the eCRFs prior to obtaining access to the system and will have their own Login/Password.

Access to clinical study information will be based on an individual's role and responsibilities.

[REDACTED] uses role-based user permissions for data entry, viewing, and reporting options. All communications between users and the EDC server are encrypted. Web servers are protected by a managed firewall. This application is designed to be in compliance with applicable regulations including 21 CFR Part 11.

The application will include programmed data consistency checks and supports manual generation of data clarifications/queries, including documentation of site responses. The application maintains a comprehensive audit trail for all data entered, including updates and queries, and documents the time that each entry occurred and who made the entry.

Principal Investigators will affirm that the data for each subject at their site is accurate and complete by way of an electronic signature.

In addition, de-identified electronically generated data will be collected from clinical fitting software. The unamended data file shall be regarded as the source.

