6.8 Safety Analyses

Adverse events will be collected prospectively following implantation according to the Clinical Investigation Plan *A post-market interventional cohort study evaluating the clinical efficacy of the Osia 2 system in the US Market*. Descriptive statistics specifically counts and percentages of device or procedure related AEs will be summarized. Any subjects who die, are treatment failures, or discontinued an intervention due to an adverse event will be summarized separately.

Adverse events (AE) will be reported for the ITT population. AEs will be tabulated with the number of events and subjects with event for each event type and overall. Rates will be reported as the number of subjects who experience at least one event during the analysis interval out of the total number of subjects with follow-up to the beginning of the analysis interval. Serious adverse events (SAEs) and will also be tabulated.

Device and procedure related AEs and SAEs, Adverse Device Effects (ADEs) and Serious Adverse Device Effects (SADEs), will also be summarized as described above. Unanticipated ADEs and SADEs (UADEs and USADEs) and adverse events leading to death or study discontinuation will be provided in listing format.

All device deficiencies will be reported in listing format.

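### A subject found during surgery to have inadequate bone fits both screen failure and treatment failure, and a failed implantation falls outside the adverse-event denominators under either label

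*Protocol*

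**What the plan says.** **Eligibility.** Protocol 7.2.2, repeated in the synopsis, excludes subjects with "Insufficient bone quality to support the BI300 implant as determined by the surgeon". It does not say whether the surgeon decides before or during the operation. The schedule in Protocol 3 marks "Inclusion/Exclusion" at Screening only. The Screening procedures in 7.3.2.2 cover histories, demographics and audiometry, and include no assessment of bone.

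**Subject status.** Protocol 7.2.5 defines a screen failure as "A consented subject that has been determined to not meet all eligibility criteria for enrolment". Enrolled/treated subjects are "Subjects who have met all eligibility criteria, have qualified for surgery and have received the Osia 2 implant". Withdrawal applies to enrolled subjects only. Protocol 14 lists the statuses that the CRF captures: consented, screen fail, enrolled/treated, withdrawn and complete. Within the enrolled/treated entry it adds: "Any participant who is not successfully implanted will be considered a treatment failure and classified accordingly".

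**Risk and safety reporting.** Protocol 8.2.2 lists as a risk "Failure of the implant to properly anchor to the skull-bone due to a lack of adequate bone quantity/quality", among other causes, and 11.2.4 treats the Section 8 items as anticipated device effects. Protocol 7.3.2.4 counts surgery as treatment and starts adverse event reporting there. SAP 6.2 defines the ITT cohort as all implanted subjects. SAP 6.6.2 assesses the safety endpoint in that cohort, and SAP 6.8 reports adverse events for it. SAP 6.8 also says: "Any subjects who die, are treatment failures, or discontinued an intervention due to an adverse event will be summarized separately". SAP 6.4 presents reasons for exclusions.

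**The concern.** There are two linked gaps.

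The first is status. If the surgeon judges the bone inadequate once the operation is under way, Protocol 7.2.2 and 7.2.5 allow the subject to be recorded as not meeting an eligibility criterion, hence a screen failure. Protocol 14 calls the same subject a treatment failure. No rule of precedence is written down. A subject booked the first way does not enter the treatment-failure summary promised in Protocol 9.9 and SAP 6.8.

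The second does not depend on the label. Events are collected from surgery onward, but the adverse-event tables and the safety endpoint use only subjects who received the implant. Someone operated on without successful implantation is exposed to the procedure, yet is absent from the denominator for procedure-related events.

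Safety is the only secondary endpoint, and with about 20 subjects one case is visible in the reported rates. Protocol 7.2.3 sets its target in newly implanted subjects, so an unsuccessful case does not count towards the 20 and a further subject can be recruited.

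**Working it through.** No figure in the plan bears on this point, so there is nothing to reproduce. The check is to trace one hypothetical subject through the written rules and then illustrate the size.

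**Tracing the subject.** Suppose a subject consents, passes Screening, and is taken to surgery. The surgeon then finds the bone inadequate and no implant is placed.

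1. *Protocol 7.2.5.* Enrolled/treated does not apply, because no implant was received. Withdrawn does not apply, because it presupposes enrolment. That leaves consented or screen failure. The screen-failure definition fits literally, since an exclusion criterion in 7.2.2 is met and the definition has no end point.
2. *Protocol 14, narrative sentence.* Implantation was not successful, so the subject is a treatment failure. There is no exception for bone quality.
3. *Protocol 14, status list.* Treatment failure is not among the five statuses. The sentence that creates it sits inside enrolled/treated, which itself requires successful implantation. The instruction to classify accordingly therefore points to no available category.
4. *Protocol 8.2.2 and 11.2.4.* If the event is recorded as a failure to anchor, it is an anticipated device effect. Anticipated describes the event and is not a subject status. Protocol 11.2 still requires such events to be reported, so this label sits alongside treatment failure without conflict.
5. *SAP 6.2, 6.6.2 and 6.8.* The subject was not implanted, so is outside ITT and outside the adverse-event tables, whichever of steps 1 and 2 is followed. Protocol 7.3.2.4 nevertheless has events collected from surgery.

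Steps 1 and 2 give two competing statuses. Step 5 gives a denominator gap that remains even if step 2 is followed.

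**Size, as illustration.** The documents give no rate of failed implantation. Assume k = 1 to 3 failures in addition to the planned 20 implanted subjects. Limits are exact Clopper-Pearson, the plan's own method for categorical data (Protocol 9.1, SAP 6.1.1).

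- Zero events in n: upper limit = 1 − 0.025^(1/n). For n = 20: 1 − 0.025^(1/20) = 16.8%.
- k events in n: lower limit = the 2.5% quantile of Beta(k, n − k + 1); upper limit = the 97.5% quantile of Beta(k + 1, n − k).

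| Assumed failures | All surgeries started (95% CI) | Failures left out (95% CI) |
|---|---|---|
| 1 | 1/21 = 4.8% (0.1% to 23.8%) | 0/20 = 0% (0% to 16.8%) |
| 2 | 2/22 = 9.1% (1.1% to 29.2%) | 0/20 = 0% (0% to 16.8%) |
| 3 | 3/23 = 13.0% (2.8% to 33.6%) | 0/20 = 0% (0% to 16.8%) |

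The same arithmetic applies to the incidence of procedure-related events if those subjects are the only ones with such an event.

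**The case against.** The best defence is that the plan, read as a whole, already answers the status question. Eligibility is checked at Screening only. Protocol 7.2.5 ties the consented status to the Screening requirements. Section 14 describes a screen failure as someone not eligible to go on to participation, which looks forward. Candidates have already been judged suitable for implantation under usual practice (7.3.2.1). The Section 14 sentence covers every participant without exception, so booking an operative failure as a screen failure would go against it. This is a fair reading and probably the intended one. It does not close the gap, because 7.2.5 is equally literal and the CRF offers no status in which to record a treatment failure.

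Three stronger readings may tempt a reader, and the documents do not support them.

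- *Three mutually exclusive classifications.* Only two compete. An anticipated device effect is compatible with treatment failure and remains reportable. The risk in 8.2.2 also covers failure to anchor from other causes, so it is not simply the eligibility judgement under another name.
- *The case would vanish.* SAP 6.4 gives reasons for exclusions, treatment failures have a separate summary, and the reduced documentation in 7.3.2.2 is worded for subjects found ineligible at the Screening visit. What can be lost is the subject's place in the treatment-failure summary and in the safety rates.
- *The trial would report a guaranteed implantation success rate.* Every enrolled subject is implanted by definition, but no success rate is a planned endpoint.

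It is also fair to say that the counts above are assumed and their intervals overlap heavily. They show how the reporting would change, not how likely that is.

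None of this defence touches the denominator gap.

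**Conclusion.** The point holds in two parts. First, a subject in whom inadequate bone is found during surgery can be given either of two statuses. Section 14 favours treatment failure, but its placement and the missing CRF status leave screen failure open. Second, and more firmly, SAP 6.2 and 6.8 confine adverse-event reporting to implanted subjects while Protocol 7.3.2.4 starts collection at surgery. A failed implantation and its procedural events are therefore outside the safety denominators even when the status is right.

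The consequence is limited to safety reporting. The primary comparison of aided and unaided performance is made in implanted subjects and does not change. The size is unknown because the plan gives no rate. With one assumed failure the contrast is 1/21 = 4.8% against 0/20, with upper limits of 23.8% and 16.8%. The plan should be changed because the correction is cheap and affects the only secondary endpoint. The documents do not show that cases would be reclassified on purpose, and no such inference is needed.

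**What to change.** - **Protocol 7.2.5 and 14.** State that screen-failure status can be assigned only before surgery starts, and that any subject in whom surgery starts without successful implantation is classified as a treatment failure. Add treatment failure to the CRF status list.
- **SAP 6.2.** Add a safety set of all subjects in whom surgery was started. Leave the ITT definition for the primary analysis as it is.
- **SAP 6.6.2 and 6.8.** Report adverse events over the safety set, and give the numbers attempted, implanted and failed, with reasons, over the same set.

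The cost is a few sentences in each document and one CRF status code. The plan already has event collection start at surgery, so no new assessment is needed. The downside is that the reported safety and implantation figures may look slightly less favourable. The change concerns classification and analysis only. It proposes no surgical or eligibility rule, and the judgement about bone stays with the surgeon.
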